Updated 04/28/2020

Statistical Analysis Plan

Identifier: NCT02414607

Study Title: Effect of Elderberry Juice on Cognition and Inflammation in Patients With Mild Cognitive Impairment

Baseline demographics and clinical characteristics

Group differences between Elderberry and Placebo control were evaluated using independent sample t-tests for continuous variables and chi-square analyses for categorical variables.

Cognitive Measures

For each outcome variable, fixed effects of group (Elderberry, Placebo control), time (baseline, 3-month follow-up; baseline, 6-month follow-up) and the group by time interaction will be tested using Multilevel Modeling (MLM) analyses in SPSS (version 27), using a first-order Autoregressive covariance structure (AR1) and restricted maximum likelihood estimation. Given the preliminary nature of the study, pairwise comparisons between groups and within groups over time will be examined for both significant effects ($\alpha \leq .05$) and trends ($\alpha < .10$).

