All researchers and clinicians taking part in this study will conduct all practices in compliance with this protocol, proceed under Good Clinical Practice (GCP), and follow all regulatory requirements outlined by University, State, and Federal agencies.

2.5 Description of the population to be studied:

When examining the impact of an agent that acts on inflammation and has antioxidant properties, targeting neuroprotection, it is important to identify and treat patients at the earliest stage. Therefore, we propose to investigate the effects of elderberry juice in patients with mild cognitive impairment, MCI. MCI is characterized by impaired memory and preserved activities of daily living (6,7). Patients with this diagnosis are at significantly increased risk for developing dementia (8-10). Most researchers propose MCI as the mildest endpoint on the spectrum of Alzheimer's disease (9). With the recent advances in treatment options for Alzheimer's disease, much attention has been directed at intervention at earlier stages. Recent research has focused on whether or not agents may delay the progression from MCI to dementia (11, 12). In addition to any delay in or prevention of progression, it would also be of interest to determine whether agents result in any cognitive benefits for MCI patients. Studies have examined to effects of cholinesterase inhibitors, the first type of drug on the market for Alzheimer's disease, on cognition and global assessment outcomes in MCI, and have revealed effects on global assessment, psychomotor speed, and attention, but not on specific memory tasks (13).

Inclusion criteria: CDR score of 0.5 and an MMSE of at least 24, as well as have no known sensitivity to elderberry products, or presence of any health condition that in the clinical experience of the investigators might impair their ability to complete the study. Recruited subjects will be aged 50 or more.

Exclusion criteria: Known history of sensitivity to elderberry products. Known allergy to honeysuckle. Current diagnosis of diabetes. Bleeding disorder. Currently pregnant. Currently making changes to other drugs that might affect cognitive performance (subjects showing the greatest cognitive decline and other signs of Alzheimer's disease may be prescribed cholinesterase inhibitors as this is a standard of care for Alzheimer's disease but not MCI). Presence of any condition the health professional believes will impair ability to complete

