Our aim is to begin to explore the potential translational impact of elderberry juice, a botanical agent. To achieve this, we will perform a pilot trial of elderberry juice in patients with mild cognitive impairment (MCI). It is critical to determine whether the course of development of Alzheimer's can be altered in this high-risk population. Our primary outcome measure will be visuospatial problem solving, as this has been shown to be sensitive to drug effects in MCI. We will also track other cognitive outcomes as well as the incidence of progression to dementia. Furthermore, we will examine inflammatory markers to begin to explore the potential mechanism of its effect. The results of this study will yield pilot data for publication and for development of a larger clinical trial for which external funds will be sought.

4. Trial Design

4.1 A specific statement of the primary endpoints:

Subjects will be assessed for changes in cognitive performance measures: CDR (for determination of progression to dementia), MMSE (general cognition), IADL (functional ability), HVLT (memory), BNT (language), Rey CFT (spatial function), anagrams (verbal cognitive flexibility), and VPS (spatial cognitive flexibility).

4.2 A description of the type/design of trial:

Double-blinded placebo-controlled pilot trial

4.3 A description of the measures taken to minimize/avoid bias:

Twenty of the subjects will be randomly assigned to receive elderberry juice and twenty control subjects will be randomly assigned to receive an equal amount of a flavored liquid with no nutritional content as a placebo control group. The clinicians will be blinded as to group, as will be the assessor. [name], a graduate student in [name] lab who is otherwise uninvolved in the study, will keep the unblinding code in case a need arises to break the code for clinical purposes or preliminary data analyses.

4.4 A description of the trial treatment(s) and the dosage and dosage regimen of the investigational product(s):

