In other research examining the effects of other anthocyanin-rich fruit extracts on MCI, a significant effect was revealed on word list memory with 12 subjects (33). In this study, the subjects in the treatment group improved their word list memory scores from 35.2 to 38.6, with a

standard deviation of less than 2. Based upon this data, the power of a study at the level of $\alpha=0.008$ (adjusted for multiple measures for the various cognitive tasks) with a sample of 13 would be 0.95 for detecting an effect of elderberry juice if it has similar effects as the grape juice on memory, and a sample of 18 would yield a power of 0.99. Therefore, we expect that the sample size of 20 per group (total 40) would be sufficient to reveal effects on word list memory (HVLT), as well as our other cognitive and behavioral outcome measures (VPS, MMSE, Rey CFT, BNT, and IADL), if their performance follows the same response as observed with word list memory. This pilot study will also yield results for the purpose of deriving power calculations for determination of appropriate sample sizes for larger, subsequent studies.

[name] and [name] see at least 80 patients with MCI each year in their clinics. Most of these patients have expressed a willingness to participate in research. We may need to enroll up to 60 subjects to obtain a sufficient set of 40.

6.3 The selection of subjects to be included in the analyses:

Subjects taking less than 75% of the scheduled dose or failing to complete at least one follow-up session will be excluded from analysis.

7. Potential Risks Related to Drug

The elderberry can cause problems for people with a known allergy in the *Caprifoliaceae* family (honeysuckle). The related side effects are given below.

- There are reports of gastrointestinal distress, diarrhea, vomiting, abdominal cramps, and weakness after drinking elderberry juice made from crushed leaves, stems, and uncooked elderberries. **Notably, toxicity typically arises from uncooked berries and preparations for this study will be carried out to minimize such reactions.**
- In theory, high doses or long-term use of elder flowers may have diuretic (urine-producing) effects. People taking diuretics or drugs that interact with diuretics should use caution when taking products containing elder.
- Elder may also lower blood sugar levels. Dizziness, headache, convulsions, and rapid heart rate have also been reported.

8. Data Handling and Recordkeeping

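### The by-visit between-group comparisons carry no covariate or baseline adjustment, so at 20 per arm a chance imbalance in age can shift them; the group-by-time contrast is largely protected

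*SAP*

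**What the plan says.** - **Baseline (SAP, Baseline demographics and clinical characteristics).** The arms are compared by test: "Group differences between Elderberry and Placebo control were evaluated using independent sample t-tests for continuous variables and chi-square analyses for categorical variables". No significance level, decision rule or consequence is attached to these tests.
- **Outcome models (SAP, Cognitive Measures).** "fixed effects of group (Elderberry, Placebo control), time (baseline, 3-month follow-up; baseline, 6-month follow-up) and the group by time interaction will be tested". The covariance is AR(1), estimation is by REML, and no covariate is listed. Baseline is one of the levels of time.
- **Contrasts (SAP, Cognitive Measures).** "pairwise comparisons between groups and within groups over time will be examined", read at 0.05 for significance and below 0.10 for trends. No adjustment for the baseline score is named.
- **Allocation (protocol 4.3).** "Twenty of the subjects will be randomly assigned to receive elderberry juice and twenty control subjects will be randomly assigned". No stratification or minimisation factor is described.
- **Population (protocol 2.5).** "Recruited subjects will be aged 50 or more", with no upper limit. Severity is narrowed by requiring a CDR of 0.5 and an MMSE of 24 or more. The MMSE is given to everyone at baseline (protocol 4.5).

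**The concern.** In a model with group, time and their interaction, the natural reading of a pairwise comparison between groups is a comparison of the two arms' estimated means at each visit. At 3 and 6 months that is a plain difference in follow-up means. If one arm happens to be older, part of the difference is age, and nothing in the model removes it.

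The baseline table does not protect against this. Under randomisation any baseline difference is due to chance, so the test answers no useful question. At 20 per arm its failure to reach significance is weak evidence of balance. At stake is the reading of a single small trial: a by-visit difference or trend could partly reflect who was allocated where. Baseline data that would remove that part, and usually sharpen the estimate, are already collected.

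**Working it through.** **The plan's own figures.** The documents give no figure for baseline imbalance. The only sample-size figures are the powers in protocol 6.2 (effect 38.6 − 35.2 = 3.4, SD 2, alpha 0.008). Reading the sample as per group, with a two-sided normal approximation, they come out at 0.954 for 13 (stated 0.95) and 0.993 for 18 (stated 0.99). They reproduce, but say nothing about baseline imbalance. The input used below is 20 per arm.

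**1. What a baseline t-test lets through.** The largest non-significant difference in SD units is t(0.975, 38) × √(2/20) = 2.024 × 0.316 = 0.640. The two-sided 0.05 level is assumed, since the SAP sets none for these tests. If 15 per arm remained after the exclusions in protocol 6.3, it would be 0.75 SD.

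**2. How often imbalance arises.** The difference in covariate means has SD √(2/20) = 0.316 in covariate SD units.
- At least 0.5 SD: 2 × [1 − Φ(0.5/0.316)] = 0.114.
- At least 0.4 SD: 2 × [1 − Φ(0.4/0.316)] = 0.206.

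**3. Effect on a by-visit contrast.** Shift = r × imbalance, where r is the correlation of the covariate with the follow-up score. Assuming r = 0.3 to 0.5 for age, a 0.5 SD imbalance gives 0.3 × 0.5 = 0.15 SD to 0.5 × 0.5 = 0.25 SD. Given that imbalance and no treatment effect, the estimate is centred on the shift with SD √[(1 − r²) × 0.1]. The chance of exceeding the 0.640 critical value in either direction is 5.6% at r = 0.3 and 7.8% at r = 0.5. At the 0.10 trend level (critical value 0.533) it is about 11% and 15%.

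**4. Effect on the group-by-time contrast.** A covariate effect that is the same at every visit drops out of change from baseline. This was simulated with 20,000 trials, no treatment effect, a covariate effect of 0.5 or 0.7 SD per SD at all visits, and a between-visit correlation of 0.7. Results among the 16% of trials whose imbalance exceeded 0.4 SD yet was non-significant on the baseline t-test:

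| Contrast | Shift | False-positive rate |
|---|---|---|
| By-visit, unadjusted | 0.25 to 0.35 SD | 9% to 10% |
| Group by time | about 0 | 4% to 5% |

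Over all randomisations both contrasts held 5%.

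Protection is not complete. A covariate that affects the rate of change still enters. If the outcome's own baseline is imbalanced by 0.5 SD, regression to the mean shifts the change contrast by (ρ − 1) × 0.5, which is −0.15 SD at a between-visit correlation ρ of 0.7. Adjusting for the baseline score removes that shift.

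**5. What adjustment gains.** The SE factor for a by-visit contrast is √(1 − r²): √0.91 = 0.954 and √0.75 = 0.866, a cut of 5% to 13% when the covariate is balanced. At a 0.5 SD imbalance the variance is multiplied by 1 + 0.25/(38 × 0.1) = 1.066, so the SE by 1.032. The factors become 0.954 × 1.032 = 0.985 and 0.866 × 1.032 = 0.894, a cut of about 2% to 11%. The overall range is therefore roughly 2% to 13%.

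For the outcome's own baseline score, relative to 1.00 for the unadjusted follow-up comparison, the variance factor is 1 − ρ² after adjustment and 2(1 − ρ) for change:
- ρ = 0.5: 0.75 adjusted, 1.00 change.
- ρ = 0.7: 0.51 adjusted, 0.60 change.

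**The case against.** The strongest reply is that the model already tests group by time with baseline as a level of time. That is the contrast that speaks to a treatment effect, and it cancels stable prognostic differences. This stands, and it confines the point to the by-visit comparisons and the group main effect. A reader might infer from the missing covariates that imbalance contaminates every between-group result; step 4 shows otherwise.

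Three further inferences also go beyond the documents.
- *That the SAP decides comparability, or selects covariates, by baseline p-value.* It attaches no rule to the tests, and its 0.05 and 0.10 levels are stated for the outcome comparisons. The 0.64 SD figure shows only what non-significance can hide.
- *That the trial's type I error is inflated.* Averaged over randomisations it is nominal; the problem is conditional on the imbalance that occurred.
- *That the chi-square tests are unreliable at this size.* The SAP lists no categorical variables, and a characteristic present in 10 to 30 of the 40 subjects has all expected counts at 5 or more.

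It is also fair to say that severity is partly restricted at entry, so age is the better example, and that a pilot of 40 cannot carry a large model. Age and MMSE, each with a visit interaction, would add six fixed effects to the present six with three visits. That argues for a short list, not for none.

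**Conclusion.** The point holds for the unadjusted by-visit comparisons. About one randomisation in nine gives an imbalance of 0.5 SD or more on a given covariate. For age that means a shift of 0.15 to 0.25 SD, with a conditional false-positive rate of about 6% to 8% at the 0.05 level. The group-by-time contrast is largely unaffected.

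This is an inexpensive improvement, not a threat to validity. It rests on 20 analysed per arm, two-sided tests, and an assumed age correlation of 0.3 to 0.5. The statement about overall type I error applies to the subjects as randomised; the adherence and follow-up exclusions in protocol 6.3 come after randomisation and are not covered by it. Removing the baseline p-values would, by itself, change no result.

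**What to change.** Amend the SAP as follows.
1. In every cognitive model, include age and, for outcomes other than MMSE, baseline MMSE as main effects, whatever balance is observed. Add visit interactions only if the sample supports them.
2. Base between-group inference on the group-by-time contrast (change from baseline), or on a follow-up comparison adjusted for the outcome's own baseline score. The second option means taking baseline out of the time factor and entering it as a covariate.
3. Report baseline characteristics as means with SDs, or counts, with standardised differences and no tests.

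The SAP describes the baseline comparisons in the past tense, so the covariates should be justified on prognostic grounds and not by those results.

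Cost: SAP wording and one or two degrees of freedom per model. No new data are needed. The SE gain for by-visit contrasts is roughly 2% to 13% and may nearly vanish if the covariate is weak or imbalanced.

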Subjects will drink 5 ml juice by mouth, diluted in 8oz of water, three times daily. Subjects will be given sufficient juice at each visit to last until the next visit. Juice containers will be clearly labeled indicating the contents as a research supplement with directions advising subjects of dose schedule. Subjects and caregivers will also be asked to check each dose on a dose log (indicating day of trial, date, time, and dose), and will bring the juice containers to the next visit to confirm that a proper amount has been administered.

4.5 Subject Involvement:

Prior to initiation of elderberry juice or placebo, baseline visit 1, subjects will be assessed with the CDR (for determination of progression to dementia), MMSE (general cognition), IADL (functional ability), HVL (memory), BNT (language), Rey CFT (spatial function), anagrams (verbal cognitive flexibility), and VPS (spatial cognitive flexibility). They will also be administered a Food Frequency Questionnaire to determine any individual differences in diet that might be relevant to the current study's findings. After initiation of elderberry juice or control, subjects will be retested at 12 weeks, visit 2, (the timeframe that revealed significant effects with other anthocyanin-rich fruit preparations (33,34), 6 months, visit 3, and (pending resubmission for second year of support) 12 months, visit 4. At each visit following baseline the Clinical Global Impression of Change (CGIC) will also be administered. Blood samples (30mL) will be obtained at baseline and each time point in the trial to determine immunological markers, 4 times total if subject progresses through all time points.

4.6 Maintenance of trial treatment randomization codes:

The clinicians will be blinded as to group, as will be the assessor. [name], a graduate student in [name] lab who is otherwise uninvolved in the study, will keep the unblinding code in case a need arises to break the code for clinical purposes or preliminary data analyses. This will be securely stored in her lab space at [name]. All subject data will be coded to a study specific code and all identifying information will be stored on a separate secure server.

6.2 The number of subjects planned to be enrolled and reason for choice of sample size:

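### The SAP's group-by-time interaction amounts to an unadjusted change-score comparison: valid under randomisation, but less precise than adjusting for the baseline score already collected

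*SAP*

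**What the plan says.** The SAP's Cognitive Measures section fits fixed effects of group and of time, where the levels of time pair baseline with the 3-month and with the 6-month visit, and "the group by time interaction will be tested using Multilevel Modeling (MLM) analyses", "using a first-order Autoregressive covariance structure (AR1) and restricted maximum likelihood estimation". Baseline is therefore part of the outcome vector, and the group term leaves each arm its own baseline mean. The same section adds that "pairwise comparisons between groups and within groups over time will be examined for both significant effects" and trends, again with no mention of baseline adjustment. Neither document names a baseline covariate, an analysis of covariance or a constraint to a common baseline mean.

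The SAP does compare the arms at baseline: "Group differences between Elderberry and Placebo control were evaluated using independent sample t-tests for continuous variables". That comparison is descriptive and does not feed into the treatment-effect model.

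The data for adjustment will exist. Protocol 4.5 states "Prior to initiation of elderberry juice or placebo, baseline visit 1, subjects will be assessed with the CDR" and goes on to list the MMSE, IADL, HVLT, BNT, Rey CFT, anagrams and VPS. Section 3 says "Our primary outcome measure will be visuospatial problem solving". Section 6.2 plans 20 subjects per group and intends the results to inform sample sizes for later studies.

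**The concern.** In a randomised trial the two arms share the same expected baseline. The most precise use of the baseline score is to weight it by its regression slope on the follow-up score. With similar SDs that slope is about r, which is below 1. The planned interaction fixes the weight at 1 whatever the data show, and so carries avoidable noise.

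With 20 per arm, the precision of the effect estimate is a real limit on what the pilot can show for effects of modest size. It also affects how well the effect estimate can inform a larger trial.

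**Working it through.** **1. The plan's own figure.** Protocol 6.2 uses a change of 38.6 − 35.2 = 3.4 points, an SD of 2 (given as an upper bound) and alpha 0.008, "adjusted for multiple measures for the various cognitive tasks". Reading n as per group, with a two-sided normal approximation and z(0.996) = 2.652:

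- n = 13: SE = 2 × √(2/13) = 0.784; 3.4/0.784 − 2.652 = 1.68; power 0.954 (stated 0.95).
- n = 18: SE = 2 × √(2/18) = 0.667; 3.4/0.667 − 2.652 = 2.45; power 0.993 (stated 0.99).
- n = 20: SE = 2 × √(2/20) = 0.632; 3.4/0.632 − 2.652 = 2.72; power 0.997 (0.993 by noncentral t).

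The stated figures reproduce. They take a within-arm change from a grape-juice study as the effect, and the text does not say whether the SD is that of the score or of the change.

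**2. What the interaction estimates.** The means are saturated (each arm has its own mean at each time). With complete data, generalised least squares then returns the observed cell means whatever the covariance. The interaction at a follow-up visit is therefore the difference between arms in (follow-up mean − baseline mean). A numerical check with AR(1) at correlations 0.5, 0.7 and 0.8 gave equality to rounding error, both with two time points and with three. The result thus holds whether the SAP intends two baseline-to-follow-up models or one three-visit model.

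**3. Variances.** Inputs: n = 20 per arm (6.2); equal SDs of 1 at baseline and follow-up (assumed); r between baseline and the visit in question (not in the documents; range assumed).

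- Change score: (2/n) × 2(1 − r).
- Adjusted: (2/n) × (1 − r²) × 37/36. The factor 37/36 is the cost of estimating the slope with 40 subjects.
- Ratio: (1 + r)/2 × 37/36. Equivalent n per arm: 20 divided by the ratio.
- Power: noncentral t, two-sided 0.05, 38 df (change) and 37 df (adjusted), for an illustrative 0.7 SD effect that is our assumption.

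| r | Change variance | Adjusted variance | Ratio | Reduction | Equivalent n per arm | Power, change to adjusted |
|---|---|---|---|---|---|---|
| 0.5 | 0.100 | 0.0771 | 0.771 | 23% | 26 | 0.58 to 0.69 |
| 0.6 | 0.080 | 0.0658 | 0.822 | 18% | 24 | 0.67 to 0.76 |
| 0.7 | 0.060 | 0.0524 | 0.874 | 13% | 23 | 0.80 to 0.85 |
| 0.8 | 0.040 | 0.0370 | 0.925 | 7.5% | 21.6 | 0.93 to 0.94 |
| 0.9 | 0.020 | 0.0195 | 0.976 | 2% | 20.5 | no visible change |

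Break-even is where (1 + r)/2 × 37/36 = 1, so r = 72/37 − 1 = 0.946. A simulation of 200,000 trials per value of r, with bivariate normal scores and 20 per arm, gave variance ratios of 0.770, 0.873 and 0.926 at r = 0.5, 0.7 and 0.8.

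In a single three-visit AR(1) model the baseline-to-month-6 correlation is the square of the adjacent-visit correlation. An adjacent correlation of 0.7 gives r = 0.49 at month 6, so the gain there is larger than at month 3.

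**4. Chance baseline imbalance.** The between-arm baseline difference has SD √(2/20) = 0.316, so an absolute difference above 0.3 SD has probability 0.34. Such a difference shifts the change-score estimate by 0.3 × (1 − r), which is 0.15 SD at r = 0.5 and 0.09 SD at r = 0.7. The variance of that shift over randomisations is (2/n)(1 − r)². Before the slope cost, the gap between the two variances is (2/n)[2(1 − r) − (1 − r²)], which is also (2/n)(1 − r)². At r = 0.5 both are 0.025. The imbalance is the source of the loss in step 3, so the two must not be added.

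**5. Restricted baseline spread.** Selection on baseline leaves the slope and residual variance unchanged but shrinks what adjustment can remove. Suppose r = 0.7 before selection and the baseline variance is halved (assumed). The change variance is then proportional to 0.51 + 0.5 × 0.3² = 0.555 and the adjusted variance to 0.51. The ratio is 0.92 before the slope cost, against 0.85 without selection.

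**The case against.** The strongest reply is that nothing here is an error. Averaged over randomisations the change-score contrast is unbiased and keeps its type I error. Change is also what protocol 4.1 says will be assessed, and the earlier VPS result that motivates the primary outcome was on change scores. All of that stands. A reader might infer that the planned test is biased or invalid, and the documents do not support that reading. Nor is baseline ignored: it enters with a weight of 1.

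The size is also open to challenge. No correlation is given, nothing in the documents excludes r of 0.9 or more, and there the gain is negligible. The 0.7 SD effect is ours; for the 6.2 planning effect power is already about 0.99, so adjustment changes nothing material. In answer, that planning effect comes from word-list memory in another study, and 6.2 carries it to VPS and the other scores only on condition that they respond in the same way. For smaller effects the precision matters.

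A reader might count chance imbalance as a second harm. It is not; step 4 of the working shows that it is the same loss.

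Two limits also stand. Entry requires an MMSE of at least 24 (2.5), so the equal-SD figures may overstate the gain for that score, and IADL may likewise vary little at baseline in this population. And the larger trial's SD and correlation can be estimated from the pilot data under either analysis; only the effect estimate loses precision.

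**Conclusion.** The point holds as one of efficiency, not validity. The planned interaction is, with complete data, an unadjusted comparison of change scores. If a subject misses one follow-up visit (6.3 keeps those with at least one) the identity becomes approximate, but the free group effect at baseline still prevents adjustment.

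On the assumptions of equal SDs, 20 per arm and r between 0.5 and 0.9, the avoidable variance is about 23% down to 2%, and it is nil near r = 0.95. Since r is not given, no single figure can be claimed. A reader might infer that the trial is underpowered for want of adjustment. The documents do not support that: on the protocol's own planning effect power is already high, and the gain matters only if true effects are smaller. This is a worthwhile, nearly free improvement to a small pilot, not the correction of a mistake.

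**What to change.** For VPS and the other scores that vary at baseline, estimate the treatment effect from a model with the month-3 and month-6 scores as outcomes and terms for group, visit, group-by-visit, baseline score and baseline-by-visit. Report the adjusted group difference at each visit with its 95% CI. Leave CDR out of this adjustment, because it is fixed at 0.5 at entry.

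A closely related alternative keeps baseline in the outcome vector and constrains the arms to a common baseline mean. The two are not identical. Under AR(1) the constrained model takes its slope from the assumed covariance, while the covariate model estimates it freely at each visit; they also differ when a visit is missing. The SAP should name one.

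The cost is one or two SAP sentences and about one degree of freedom per baseline term, two in all. No further data or subjects are needed.

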Twenty of the subjects will be randomly assigned to receive 5 ml elderberry juice by mouth, diluted in 8oz of water three times daily. The juice will be obtained from River Hills Harvest. Twenty control subjects will receive an equal amount of a flavored liquid with no nutritional content as a placebo control group. The placebo liquid will match the elderberry juice closely in color using commercially available colorants. Subjects will be allowed to mix the juice in 8oz of water if the bitterness of the juice makes it unpalatable. The clinicians will be blinded as to group, as will be the assessor. [name], a graduate student in [name] lab who is otherwise uninvolved in the study, will keep the unblinding code in case a need arises to break the code for clinical purposes or preliminary data analyses. Subjects will be given sufficient juice at each visit to last until the next visit. They will be provided a liquid medicine measuring spoon and instructed to measure out 5ml per dose. Subjects and caregivers will be asked to check each dose on a dose log, and bring back the used juice containers at each visit to confirm that a proper amount has been taken, as monitored by the assessor. Subjects taking less than 75% of the scheduled dose will be excluded.

After initiation of elderberry juice or control, subjects will be retested at 12 weeks, visit 2, (the timeframe that revealed significant effects with other anthocyanin-rich fruit preparations (33,34), 6 months, visit 3, and (pending resubmission for second year of support) 12 months, visit 4. The

need for pursuing follow-up at 12 months is to maximize the sensitivity for detecting incidence of progression to dementia with the CDR. Additionally at visits 2, 3, and 4 subjects will also be assessed with the Clinical Global Impression of Change (CGIC), which is a valid and reliable research tool for overall assessment of salient changes in patients (39), in which the blinded clinician rates the degree of change in the patient from the beginning of the study. The subject/caregiver will be given time to ask any questions and the clinician will be sure the subject/caregiver understands all instructions before dispensing liquid.

2.4 A statement that the trial will be conducted in compliance with the protocol:

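### The SAP plans no per-arm estimate of progression to dementia, and the AR(1) linear model that might cover CDR does not suit a score fixed at 0.5 at entry

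*SAP*

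**What the plan says.** Protocol section 3 names the primary outcome, "Our primary outcome measure will be visuospatial problem solving", and adds: "We will also track other cognitive outcomes as well as the incidence of progression to dementia". Section 4.1 opens its endpoint list with CDR and gives the reason: "Subjects will be assessed for changes in cognitive performance measures: CDR (for determination of progression to dementia". Section 2.5 requires for entry a "CDR score of 0.5 and an MMSE of at least 24", and section 4.5 has CDR assessed at baseline visit 1. Section 2.3 says the "need for pursuing follow-up at 12 months is to maximize the sensitivity for detecting incidence of progression to dementia with the CDR"; that visit depends on further funding.

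The SAP, under Cognitive Measures, sets out one model: "For each outcome variable, fixed effects of group (Elderberry, Placebo control), time (baseline, 3-month follow-up; baseline, 6-month follow-up", plus the group-by-time interaction, "using a first-order Autoregressive covariance structure (AR1) and restricted maximum likelihood estimation". It adds that "pairwise comparisons between groups and within groups over time will be examined for both significant effects" at .05 and for trends at .10. It neither names CDR nor exempts it. Its only categorical method, chi-square, stands under the heading for baseline characteristics.

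**The concern.** There are two parts, and only the second is conditional.

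**No progression estimate.** If CDR goes into the model, the output is a mean score per arm and visit. If it does not, CDR has no planned analysis. On either reading the SAP does not say how many subjects progressed in each arm, nor which CDR value counts as progression. Section 3 wants pilot data for a larger trial, and that trial would lack a stated progression estimate per arm.

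**A poor fit if CDR is modelled.** Every subject starts at 0.5, so CDR has no between-subject variance at baseline. AR(1) assumes the same variance at every visit. Averaging a zero variance with a positive one understates the spread at follow-up, so a by-visit comparison of the arms can look more certain than it is.

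**Working it through.** The documents give no standard error, variance or progression rate for CDR, so there is no figure of the plan's own to reproduce. The section 6.2 power figures concern word list memory and do not bear on this.

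**Inputs.** 20 per arm (section 6.2); CDR 0.5 for all at baseline (sections 2.5 and 4.5); AR(1), REML, and time as baseline/3-month and baseline/6-month pairs (SAP). Assumed: complete data, two-sided tests, and progression meaning CDR of at least 1. All progression rates are assumptions.

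**Two-visit fit.** Let v be the true within-arm variance at follow-up. The within-arm covariance matrix is diag(0, v).
- For a given rho, REML gives s² = v / [2(1 − rho²)].
- The profiled criterion is then a constant − log(1 − rho²), which is smallest at rho = 0. So rho = 0 and s² = v/2.
- By-visit comparison: model SE / true SE = √(s²/v) = √0.5 = 0.707, which is 29% too small.
- Interaction: model variance of a change is 2s²(1 − rho) = v, the true value. Ratio 1.
- Group main effect: model variance of the two-visit mean is s²(1 + rho)/2 = v/4, the true value. Ratio 1.

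**Type I error of the by-visit comparison at nominal .05.** In large samples it is 2[1 − Φ(1.96 × 0.707)] = 0.166. Exact enumeration with 20 per arm and nobody reverting to CDR 0:

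| Assumed progression rate | Type I error |
|---|---|
| 1% | 2.8% |
| 1.5% | 5.3% |
| 2.5% | 10.7% |
| 5% | 20.2% |
| 7.5% | 23.0% |
| 10% | 22.7% |
| 20% | 18.4% |
| 30% | 15.8% |

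The interaction stays at 0.2–5.3% over rates of 2.5–30%. When some subjects revert to CDR 0, the by-visit error is roughly 15–20% in the cases tried; for example, it is 17% with 15% reverting and 10% progressing.

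**Example: 0 v 2 progressors of 20, nobody reverting.**
- Sum of squares in the second arm: 20 × 0.1 × 0.9 × 0.5² = 0.45. So v = 0.45/38 = 0.01184 and s² = 0.00592.
- By-visit: SE = √(0.00592 × 2/20) = 0.0243; difference 0.05; t = 2.05; p = 0.047 (df 38) or 0.043 (df 76).
- Interaction: SE = √(0.01184 × 2/20) = 0.0344; t = 1.45; p = 0.15.
- Fisher: 2 × C(20,2)/C(40,2) = 380/780 = 0.49. Exact 95% CI for the difference in proportions: about −8 to +32 points.

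**Same split with one reverter in each arm.** The sums of squares are 0.2375 and 0.7375, so v = 0.975/38 = 0.02566. By-visit SE = √(0.01283 × 2/20) = 0.0358; t = 1.40; p = 0.17.

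**Single three-visit model.** With an assumed 6-month to 3-month variance ratio of 0.5–3 and a follow-up correlation of 0–0.9, the 6-month by-visit SE is 0–33% too small (type I error 5–19%). In the covariances tried for 3 months, the SE ratio was 0.80–0.89 when the 3-month variance was 70–100% of the 6-month variance, 1.0 when it was half, and about 1.2 when it was 30%. The exact result for the interaction belongs to the two-visit fit; in the three-visit cases its SE also moved either way.

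**The case against.** The SE defect needs several things at once: CDR in the linear model, between-group comparisons made by visit, separate two-visit fits, and complete data. The first is unsettled. Section 4.1 and the SAP's reference to every outcome point to yes. Section 6.2 names six measures without CDR and uses alpha 0.008, about 0.05/6, which points to no. This stands, and the SE result has to stay conditional.

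A reader might infer that two progressors against none would simply be declared significant. The documents do not support that as a general statement: one reverter in each arm moves p from 0.047 to 0.17, and nothing in the plan rules out reversion. The SE ratio of 0.707 does survive reversion.

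It can also be said that if CDR only takes the values 0.5 and 1, the fitted mean gives the progression proportion as 2 × (mean − 0.5), so the gap is one of reporting. That is true in that case only. With reversion to 0 or scores above 1 the mean no longer identifies the proportion, and the SAP does not plan the conversion anyway.

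Finally, this is a pilot, and section 2.3 ties sensitivity for progression to a 12-month visit that is not yet funded. That partly explains thin planning at 3 and 6 months. It does not remove the undertaking in section 3.

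**Conclusion.** The point holds as a minor one. The progression gap does not depend on how the SAP is read: it plans no per-arm count or proportion and no definition of progression. The SE result is conditional. If CDR is modelled in baseline/follow-up pairs with complete data, the by-visit between-group SE is 29% too small and type I error at nominal .05 is about 11–23% for assumed rates of 2.5–30%. Without reversion there is no inflation below about 1.5%. In a single three-visit model the 6-month SE is 0–33% too small under the assumed covariances, and the 3-month SE can err either way or be correct.

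Two wider readings should be resisted. The defect does not invalidate every test from the model: in the two-visit fit the interaction and group main effect have correct SEs. Nor does it touch VPS, the primary outcome in section 3; it rests on the entry restriction on CDR.

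**What to change.** In the SAP:
- Take CDR out of the AR(1) linear model and name the variables that the model does cover.
- State the CDR cut-off that defines progression, since the documents give none.
- At 3 and 6 months, report progression as counts and proportions per arm with an exact 95% CI for the difference, labelled secondary and descriptive.
- Treat Fisher's test as optional. It is conservative at this size (exact size at most 2.5% at nominal .05 over the assumed rates of 2.5–30%; 0 v 5 of 20 is needed for p < .05), so the interval should carry the interpretation.

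The cost is a few lines of text and one small table. The intervals will be wide, as the 0 v 2 example shows, which is a fair picture of what 20 per arm can say about progression.
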